## **19.2 Description of Statistical Methods**

Suggested statistical approach in more detail.

A model-based approach to hypothesis testing will be applied. This allows incorporation of complexities such as repeated measurements, nested classification factors, unbalanced observations, and determination of the magnitude of effects [Harrell]. The chosen model belongs to the family of linear mixed-effects models [Pinheiro], and it is formulated as follows:

$$\mathbf{y}_{ij} = \mathbf{X}_{ij}\boldsymbol{\beta} + \mathbf{Z}_{i,j}\mathbf{b}_i + \mathbf{Z}_{ij}b_{ij} + \epsilon_{ij}, \quad i = 1, \dots, M, \quad j = 1, 2$$

$$\mathbf{b}_i \sim N(0, \boldsymbol{\Psi}_1), \quad b_{ij} \sim N(0, \sigma_2^2), \quad \epsilon_{ij} \sim N(0, \sigma^2 \mathbf{I})$$

where  $\mathbf{y}_{ij}$  is the measured peak pressures for subject  $i$  from a sample of size  $M$ , at anatomic location  $j$  (corresponding to chest and pelvis.) The fixed-effects treatment contrast matrices  $\mathbf{X}_{ij}$  encode the experimental factor pillow type (new versus standard).  $\mathbf{Z}_{i,j}$  represents the design matrices of the level-1 random effects for subject  $i$  on the measurements for anatomic location  $j$  within subject  $i$ .  $\mathbf{Z}_{ij}$  represents the design matrices of the level-2 random effects for anatomic location  $j$  within subject  $i$ . The normally distributed  $\mathbf{b}_i$  are assumed to be independent for different  $i$ ; and the normally distributed  $b_{ij}$  are assumed to be independent for different  $i$  or  $j$  and to be independent from  $\mathbf{b}_i$ ; finally, the within-group errors  $\epsilon_{ij}$  (which represent all the variability which is not explained by the model) are assumed to be independent for different  $i$  or  $j$  and to be independent from the random effects. The parameters to be estimated by the above model are represented by the 2-vector  $\boldsymbol{\beta}$ , the variance  $\sigma_2^2$ , and the entries of the 2x2 matrix  $\boldsymbol{\Psi}_1$  (it should be noted that since the latter is a covariance matrix which is forced to be positive definite by construction, only 2 entries need to be estimated.) The total number of parameters is therefore 5.

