### 19.2.1 The Number of Participants

Due to the lack of available information in published sources to determine the effect sizes required for sample size calculation, and due to the complexity of the experimental design, no formal power analysis is possible.

However, a heuristic approach will be applied [Harrell] based on the complexity of the model used to test the experimental hypotheses, namely that the sample size should be of the order of 10 times the number of parameters estimated by the model. With the previous definition of the model complexity, we estimate the sample size to be of the order of  $M = 50$ .

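### The count of 5 model parameters, the only basis given for 50 participants, is wrongly derived: one covariance entry is dropped without reason and the residual variance is left out

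*Combined protocol and SAP*

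**What the plan says.** Section 19.2 sets out a linear mixed-effects model for peak pressure. It has a fixed-effects vector β, subject-level random effects with covariance matrix Ψ₁, a location-within-subject random effect with variance σ₂², and a residual with variance σ².

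The list of what is estimated begins "The parameters to be estimated by the above model are represented by the 2-vector" β. It then adds σ₂² and the entries of the 2x2 matrix Ψ₁. Because Ψ₁ is "forced to be positive definite by construction", the section says, "only 2 entries need to be estimated". It concludes: "The total number of parameters is therefore 5". The residual errors are described as those "which represent all the variability which is not explained by the model", but their variance is not in the list. Of the matrix Z_{i,j} the section says that it "represents the design matrices of the level-1 random effects for subject" i; its columns are not given.

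Section 19.2.1 states that a power calculation cannot be done. It applies instead the rule that "the sample size should be of the order of 10 times the number of parameters estimated by the model", and then says: "With the previous definition of the model complexity, we estimate the sample size to be of the order of" M = 50. Section 9.2 repeats the rule and the figure of 50. No other basis for 50 appears.

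**The concern.** Two steps in the count look wrong.

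- **Ψ₁.** Positive definiteness is an inequality constraint. It narrows the values that the entries may take but does not fix any of them. Going from 3 entries to 2 needs a declared restriction, such as a diagonal or compound-symmetric matrix. The section gives no such restriction and no other reason.
- **σ².** The residual variance is unknown and is estimated with the rest. The section already counts the other variance components, so leaving this one out is inconsistent with its own approach.

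The count is the sole support for the sample size, so the reader is given a ratio of 10 participants per parameter that the written model does not have. There is also a practical consequence. With neither the columns of Z_{i,j} nor the structure of Ψ₁ stated, two analysts could follow section 19.2 and fit different models. The standard error of β₂, which is tested at 0.01, and the Akaike Information Criterion that will be reported both depend on that choice.

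**Working it through.** **Inputs.** From section 19.2: β has 2 elements, Ψ₁ is 2x2, σ₂² and σ² are scalars. From section 19.2.1: 10 participants per parameter, M = 50. From section 6.4.5: 3 repeats per pillow set. With 2 pillows and 2 locations this gives 2 × 2 × 3 = 12 observations per participant.

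**1. The plan's figure.** 2 (β) + 1 (σ₂²) + 2 (Ψ₁) = 5, and 10 × 5 = 50. The sum reproduces; the error is in what is counted.

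**2. Entries of Ψ₁.** A symmetric k × k matrix has k(k + 1)/2 free entries; for k = 2 this is 2 × 3/2 = 3. Positive definiteness requires only that the squared covariance be less than the product of the variances. With both variances equal to 1 and covariance c, the eigenvalues are 1 − c and 1 + c:

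| c | Eigenvalues |
|---|---|
| −0.5 | 0.5, 1.5 |
| 0 | 1, 1 |
| 0.5 | 0.5, 1.5 |
| 0.9 | 0.1, 1.9 |

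All four matrices are positive definite, so the covariance remains a free parameter.

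**3. Recount from the model as written.**

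- Unrestricted Ψ₁: 2 + 3 + 1 + 1 = 7; 50/7 = 7.1 per parameter.
- Declared two-parameter Ψ₁: 2 + 2 + 1 + 1 = 6; 50/6 = 8.3 per parameter.

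**4. Can all of these be estimated?** That depends on the columns of Z_{i,j}. The covariance matrix of one participant's observations was differentiated with respect to each covariance parameter, and the rank of the derivatives was taken. The rank plus the 2 fixed effects gives the number estimable. Results were the same with 12 observations per participant and with 4 (one repeat).

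| Level-1 effects | Unrestricted Ψ₁ (7 written) | Diagonal or compound-symmetric Ψ₁ (6 written) |
|---|---|---|
| Intercept plus pillow | 5 + 2 = 7 | 4 + 2 = 6 |
| Pillow-specific | 5 + 2 = 7 | 4 + 2 = 6 |
| Intercept plus location | 4 + 2 = 6 | 4 + 2 = 6 |
| Location-specific | 4 + 2 = 6 | 3 + 2 = 5 |

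**5. Does any reading rescue 5?** Two readings reach the number, but neither supports the derivation. With location-specific effects and a two-parameter Ψ₁, 5 are estimable only because σ₂² cannot be separated from Ψ₁, yet the section counts both. With Ψ₁ equal to one variance times the identity, and σ² counted, the total is 2 + 1 + 1 + 1 = 5, but Ψ₁ then has 1 entry, not the stated 2.

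**6. Effect of the unstated structure on the test of β₂.** For illustration, assume balanced data, both Ψ₁ variances 1 and σ² = 1. Each pillow mean uses 6 observations per participant, and the location effects cancel in the pillow difference.

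- Intercept plus pillow: SE = √[(1 + 2 × 1/6)/50] = √(1.333/50) = 0.163.
- Either location design: SE = √[(2 × 1/6)/50] = √(0.333/50) = 0.082.

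The variances are assumed, since the documents give none. The point is only that the choice of Z_{i,j} can matter a good deal.

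**The case against.** The strongest reply is that nothing turns on the number. The rule is offered as an approximate heuristic, and ratios of 7.1 or 8.3 are not far from 10 on such a scale. That stands: the recount does not show that 50 is inadequate. Ten times the corrected count would be 60 or 70, but this is not a power-based requirement and should not be read as one.

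A second reply is that the section does say that 2 entries are estimated, so a two-parameter Ψ₁ may have been intended and merely badly explained. On that reading the count is 6, because σ² is still missing. For this reason 7 is best seen as the upper end of a range of 6 to 7.

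Third, the location-based designs are less natural readings, since location already has its own level-2 effect and a 2x2 Ψ₁ fits most easily with an intercept and a pillow effect. That is fair, but the section does not list the columns, so those designs cannot be excluded.

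Finally, one may say that residual variance is a nuisance parameter and is not normally counted. The section counts other variance components, and the rule as stated refers to all parameters that the model estimates. Even without σ², an unrestricted Ψ₁ gives 2 + 3 + 1 = 6, not 5.

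**Conclusion.** The concern holds. Positive definiteness does not reduce Ψ₁ to 2 entries, and σ² is omitted from the list of estimated parameters. The model as written has 7 parameters with an unrestricted Ψ₁, or 6 with a declared two-parameter Ψ₁. Where the level-1 effects are by location, some of these cannot be separated, and the estimable number is 6 or, in one case, 5. The participants-per-parameter ratio at M = 50 is therefore about 7.1 to 8.3 on the counts as written, against the stated 10.

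The counts follow from the model equation and need no outside figure; the estimable numbers also assume the observation layout in section 6.4.5 and the listed choices of Z_{i,j}. Adequacy of 50 is neither shown nor refuted, because the documents give no effect size or variance. The error should be corrected, since it lies in the only rationale for the sample size and hides an unspecified random-effects structure.

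**What to change.** In section 19.2:

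- delete the argument from positive definiteness;
- state the columns of Z_{i,j};
- state the structure of Ψ₁ (unrestricted, diagonal, compound-symmetric or other), which is for the authors to choose;
- add σ² to the list of estimated parameters;
- do not count σ₂² separately if the chosen structure makes it redundant;
- correct the total.

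In sections 9.2 and 19.2.1, keep 50 but do not present it as the result of 10 per parameter. Report the ratio that the corrected count p gives, for example: *The model has p estimated parameters, so M = 50 provides about 50/p participants for each.* That is 7.1 for p = 7 and 8.3 for p = 6.

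The cost is a few lines of text and no additional participants. The hypothesis tested through β₂ is unchanged. Its standard error does depend on the structure chosen, so that choice should be fixed before the data are analysed.

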### 19.2.1 The Number of Participants

Due to the lack of available information in published sources to determine the effect sizes required for sample size calculation, and due to the complexity of the experimental design, no formal power analysis is possible.

However, a heuristic approach will be applied [Harrell] based on the complexity of the model used to test the experimental hypotheses, namely that the sample size should be of the order of 10 times the number of parameters estimated by the model. With the previous definition of the model complexity, we estimate the sample size to be of the order of  $M = 50$ .

### 19.2.2 The Level of Statistical Significance and Model Validation

Considering the small sample size and the complexity of the model, a significance level of 0.01 will be considered for rejection of the null hypotheses of no difference between peak pressures (as represented by parameter  $\beta_2$ ), with the aim to control the false discovery rate [Harrell]. However, since it is generally recognised that statistical significance alone doesn't necessarily provide a realistic picture of the underlying processes generating the data [Harrell], other

measures of quality of the statistical inference will be reported, namely approximate confidence intervals, Akaike Information Criterion, and analysis of residuals.

#### **19.2.3 Procedure for Accounting for Missing, Unused, and Spurious Data.**

The chosen statistical methods can be applied even with unbalanced observations (i.e. outcomes need not be observed for all possible combinations of the experimental factors pillow and position) [Pinheiro]. Due to the nature of the experimental design and the type of measurements involved, no missing, unused, or spurious data are expected.
